#### **4 RANDOMIZATION**

The study will be randomized 2:1 UNEX-42 to placebo. Within each dose cohort, subjects will be randomly allocated to receive UNEX-42 or placebo through the Interactive Response Technology using a centrally administered block randomization.

#### **5 SEQUENCE OF PLANNED ANALYSES**

Unblinding of all data from the Post-treatment and Long-term Outcome Phases will occur after the database has been locked.

#### **6 SAMPLE SIZE CONSIDERATIONS**

No formal sample size calculations were performed.

#### **7 ANALYSIS POPULATIONS**

No analysis populations will be specified. All enrolled subjects will appear in the listings unless otherwise specified.

#### **8 GENERAL CONSIDERATIONS FOR DATA ANALYSES**

All the data collected in the electronic Case Report Form (eCRF) will be listed. In general, listings will be sorted by subject number and scheduled assessment (if applicable). Listings will include assessment date, assessment time (if available), study day, and all relevant data collected in the eCRFs. For data collected on a fixed schedule, the assessment identifier or the nominal time point will also be included on the listing. Repeat or redundant observations within an assessment window and observations that do not fall within any predefined assessment window will be flagged in these listings.

## **8.1 PREMATURE DISCONTINUATION AND MISSING DATA**

A subject's parent/guardian may voluntarily withdraw the subject, or the subject may be withdrawn from the study and/or study drug by the Investigator at any time for reasons including, but not limited to, the following:

- The subject's parent/guardian wishes to withdraw the subject from further participation.
- Any medically appropriate reason, in the opinion of the Investigator, or significant protocol violation likely to undermine the validity of results.
- The Sponsor terminates the study.

All available data from all subjects will be used as detailed in this analysis plan. No imputation for missing data will be performed.

## **8.2 MULTIPLE COMPARISONS AND MULTIPLICITY**

No inferential analyses are planned.

## **9 STUDY POPULATION**

Unless otherwise specified, all subjects will appear in the listings.

### **9.1 SUBJECT ACCOUNTABILITY**

The listing of subject disposition will include the subject number, treatment group, date/time of randomization, dates of last Post-treatment Phase and last Long-term Outcome Phase assessments, reason for study discontinuation, and dates of hospital discharge and neonatal intensive care unit discharge.

### **9.2 ELIGIBILITY CRITERIA**

The status of the entry criteria will be listed for all subjects. The listing will include the date of the initial screening assessment, whether all eligibility criteria were met (Yes/No), and a list of any specific entry criteria not met.

### **9.3 PROTOCOL DEVIATIONS**

Protocol deviations will be documented throughout the study. All deviations will be reviewed by the clinical team and those that might affect subject safety or efficacy outcomes will be considered 'Major.' All other deviations will be classified as 'Minor.' Protocol deviations will

be listed, including the date of the deviation, the type of deviation, the severity of the deviation (Major/Minor), and a description of the deviation.

## **9.4 OTHER DESCRIPTIONS OF STUDY POPULATION**

### **9.4.1 Demographics**

The listing of subject demographics will include the subject number, treatment group, date of birth, postnatal age (days), GA at birth (weeks/days), sex, race, and ethnicity.

### **9.4.2 Maternal History**

The listing of maternal history will include the subject number, treatment group, maternal age, maternal race, maternal ethnicity, reason for delivery, mode of delivery, receipt of IV magnesium during pregnancy, diagnosis of chorioamnionitis during pregnancy, and any recorded medications received during pregnancy/delivery.

### **9.4.3 Infant Measurements**

The listing of infant measurements will include the subject number, treatment group, assessment date, weight (g), length (cm), and head circumference (cm).

### **9.4.4 Infant Medical Conditions**

The listing of infant medical conditions will include the subject number, treatment group, medical condition, date started, date stopped, and whether the medical condition was ongoing at the end of the study.

### **9.4.5 Concomitant Medications**

All concomitant medications recorded on the eCRF will be mapped to a standard name and Anatomical Therapeutic Chemical (ATC) Levels 1 to 4 using the World Health Organization WHODrug Global drug dictionary. The ATC Levels 2 and 4 and verbatim term of all concomitant medications will be listed for all subjects. This listing will include the date started (or indication that drug was ongoing at randomization), date discontinued (or indication that drug was ongoing at end of Post-treatment Phase), and the condition(s) treated/indication(s). If ATC Level 4 is not available for a medication, ATC Level 3 will be substituted. If ATC Level 3 is not available, ATC Level 2 will be substituted. If ATC Level 2 is not available, ATC Level 1 will be substituted.

## 10 EFFICACY ANALYSES

Only listings will be provided. No summaries or inferential analyses will be conducted.

### 10.1 BPD ASSESSMENT

The listing for the BPD assessment at 36 weeks PMA will include the subject number, treatment group, date of assessment, whether BPD occurred, the severity of BPD (mild, moderate, severe), and predefined complications of prematurity during the Post-treatment Phase (diagnosis of sepsis, pneumothorax, clinically significant patent ductus arteriosus requiring treatment or ligation, necrotizing enterocolitis requiring treatment or surgery, intraventricular hemorrhage [including highest grade], periventricular leukomalacia, and retinopathy of prematurity [including stage]). The dates started/stopped will also be included for the predefined complications of prematurity, if available and indication of ongoing if known.

Additionally, a listing of Respiratory Severity Score will be provided. It will include the subject number, treatment group, date/time of assessment, Respiratory Severity Score, mean airway pressure, and fraction of inspired oxygen.

### 10.2 POST-NATAL STEROIDS

The listing of post-natal steroids will include the subject number, treatment group, steroid taken, date started or ongoing at randomization, date stopped or ongoing at end of Post-treatment Phase, dose, form, unit, frequency, route, and condition treated/indication.

### 10.3 GENERAL HEALTH ASSESSMENT

The general health assessment listing will include the subject number, treatment group, nominal time point, date/time, person interviewed, and the response to each question at the assessment.

## 11 SAFETY ANALYSES

The safety data collected in this study will be presented in listings. No summaries or inferential statistical analyses are planned. Assessments are treatment-emergent if they occur on or after the infusion of study drug.

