**3.3.2.4 Adverse Events**

All AEs will be documented from the time of informed consent until the time screen failure is documented, or until the subject is either discontinued from the study or all 40 Weeks PMA/Hospital Discharge assessments have been completed and should be followed until either resolution (or return to normal or baseline values), until they are judged by the Investigator to no longer be clinically significant, or for at least 30 days if the AE extends beyond the Post-treatment Phase.

All AEs meeting the criteria for serious (ie, serious adverse events [SAEs]) should be followed until resolution, death, or the subject is lost to follow-up even if they are ongoing more than 30 days after completion of the Post-treatment Phase

Refer to Section 9.1 for detailed definitions of safety events. All AEs/SAEs that occur during the study will be followed as instructed in Section 9.3.

If, at any time, the parent/guardian withdraws their consent for the subject to remain in the study, any AEs/SAEs that occur from UNEX-42 treatment (including product use errors, product quality problems, and therapeutic failures) will be reported. These events will not be recorded in the electronic Case Report Form (eCRF).

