### **7.1 SCREENING**

Screening can begin up to 48 hours prior to Baseline. Site personnel may conduct Pre-screening assessments prior to a subject's parent/guardian signing an Informed Consent Form (ICF). Pre-screening assessments may include review of the hospital data to identify potential subjects that may be eligible for the study. Screening assessments will be conducted in the hospital as inpatient assessments after informed consent has been obtained according to Table 3-1.

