## **9 ADVERSE EVENT REPORTING**

### **9.1 DEFINITIONS**

#### **9.1.1 Adverse Event**

An AE is any untoward medical experience occurring to a subject during a clinical study whether or not it is related to study drug. An AE may include an intercurrent illness, injury, or any other concomitant impairment of the subject's health, as well as abnormal laboratory findings if deemed to have clinical significance. AEs may also include worsening of an existing symptom or condition, or post-treatment events that occur as a result of protocol-mandated procedures (eg, exacerbation of a pre-existing illness following the start of the study or an increase in the frequency or intensity of a pre-existing episodic event or condition).

Thus, no causal relationship with the study drug is implied by the use of the term "adverse event."

An AE does not include the following:

- Medical or surgical procedures, as the condition for which the surgery is required may be an AE.
- Planned surgical measures permitted by the study protocol and the condition(s) leading to these measures are not AEs.
- Day-to-day fluctuations of a pre-existing disease or condition that was present or detected at the start of the study that do not worsen.

Specific complications of prematurity will be assessed from Baseline to 40 Weeks PMA/Hospital Discharge as described in Section 3.3.2.5. Therefore, the complications of prematurity should only be recorded as an AE or SAE if the event is unusual with respect to intensity, frequency,

duration as compared with symptoms in the subject's medical history, or if there is a reasonable possibility that the event was caused by the study drug. Congenital disorders should be recorded as medical history, even if diagnosed after the subject has entered the study.

Investigators should use the NCI-CTCAE Version 5.0 as guidance to grade the severity/intensity of all events. If a CTCAE criterion does not exist, the Investigator should grade the severity/intensity according to the following criteria:

- Grade 1 (mild): does not interfere with the patient's usual function
- Grade 2 (moderate): interferes to some extent with patient's usual function
- Grade 3 (severe): interferes significantly with patient's usual function
- Grade 4 (life-threatening): results in a threat to life or in an incapacitating disability
- Grade 5 (death): results in death

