## **9.2      DOCUMENTATION OF ADVERSE EVENTS**

An AE or SAE occurring during the study must be documented in the subject's source documents and in the eCRF. Information relating to the AE such as onset and cessation date, intensity, seriousness, relationship to study drug, and outcome is also to be documented in the eCRF (see Section 15.1 for definitions). Where possible, AEs should be recorded using standard medical terminology. The Investigator should attempt, if possible, to establish a diagnosis based on the presenting signs and symptoms. If several signs or symptoms are clearly related to a medically defined diagnosis or syndrome, the diagnosis or syndrome should be recorded in the eCRF, not the individual signs and symptoms.

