## 15 APPENDICES

### 15.1 GUIDELINES AND DEFINITIONS FOR RECORDING ADVERSE EVENTS

The Principal Investigator or a designated member of his/her staff will probe each subject's parent/guardian for any adverse events (AEs) that may have occurred. The Investigator should always ask the same question when conducting the verbal probe in order to ensure uniformity between subjects. The Investigator should ask:

“How is the subject doing (feeling)?”

Based on the parent/guardian's response to this question, the Investigator should ask additional questions relevant to the specific complaint, such as:

“How severe is/was the symptom?”

“How often did the symptom occur?”

“How long did the symptom last?”

It is the Investigator's responsibility to review the results of all diagnostic and laboratory tests as they become available and ascertain if there is a clinically significant change from Baseline. If the results are determined to be a clinically significant change from Baseline, this should be reported as an AE. The Investigator may repeat the diagnostic procedure or laboratory test or request additional tests to verify the results of the original tests. When possible, a diagnosis associated with the abnormality should be used as the reported AE.

Using provided definitions, the Investigator will then:

1. Rate the intensity and seriousness of the AE
2. Estimate the causality of the AE to study drug
3. Note actions taken to counteract the AE.

Definitions of Intensity, Seriousness, Causality, and OutcomeINTENSITY

An assessment of the relative intensity (severity) of an AE should be based on the NCI-CTCAE, Version 5.0. The maximum intensity encountered during the evaluation period should be checked. The assessment of intensity should be independent of the assessment of the seriousness of the AE.

SERIOUSNESS

A serious adverse event (SAE) is one that represents an actual or potential significant hazard. This includes, but is not limited to, an event that is fatal, life-threatening, permanently or severely disabling, requires or prolongs inpatient hospitalizationa, is a congenital abnormality or is medically significant (important medical events that may not result in death, be life-threatening, or require hospitalization may be considered a SAE when, based upon appropriate medical judgment, they may jeopardize the subject and may require medical or surgical intervention to prevent 1 of the outcomes listed in this definition).

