aHospitalizations that would not be considered SAEs include those for:

- Routine treatment or monitoring of the study indication not associated with any deterioration in condition.
- Treatment which was elective or preplanned, for a pre-existing condition not associated with any deterioration in condition (eg, preplanned operation which does not lead to further complications etc).
- Treatment of an emergency, in an outpatient setting for an event not fulfilling any of the definitions of serious as given above and not resulting in hospital admission.

CAUSALITY

An estimate of causality between a specified AE and the study drug is made by the Investigator. Several factors should be considered when determining causality. These factors include temporal relationship to the study drug.

- Definitions of the causality categories are as follows:
  - NOT RELATED – There is not a temporal relationship to study drug administration (too early, or late, or study drug not taken), or there is a reasonable causal relationship between another drug, or concurrent disease and the SAE, or any of the following:

- An event that precedes the first administration of study drug
- An event for which the cause is clearly related to an external event
- Temporal relationship to study drug is atypical
- Is readily explained by an intercurrent illness AND has an expected level of severity, duration, and resolution
- An alternative explanation (concomitant drug, intercurrent illness) is likely.
- POSSIBLE – There is a reasonable causal relationship between the study drug and the SAE, or any of the following:
  - Has a reasonable temporal relationship to study drug
  - The event has a plausible biological link to the activity of the study drug
  - Is unlikely to be related to an intercurrent illness or has an unexpected degree of severity, duration, or complication.
- PROBABLE – There is a reasonable causal relationship between the study drug and the SAE, or any of the following:
  - Has a reasonable temporal relationship to study drug
  - The event has a plausible biologic link to the activity of the study drug
  - Not readily explained by an intercurrent illness
  - Not readily explained by external event.

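### SAP 11 has no rule for an adverse event that starts before the infusion and worsens after it, so such an event can be listed as not treatment-emergent

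*SAP*

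**What the plan says.** SAP 11 sets the rule: "Assessments are treatment-emergent if they occur on or after the infusion of study drug". SAP 11.2 then adds a treatment-emergent indicator to each event in the adverse event listing. The protocol uses the term for a primary endpoint (10.3.1) and in the dose-limiting toxicity section (6.3) but does not define it.

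Four parts of the protocol decide what that rule acts on:

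- **Collection period.** Section 3.3.2.4: "All AEs will be documented from the time of informed consent". Section 7.1: "Screening can begin up to 48 hours prior to Baseline". An event can therefore be on record before the infusion.
- **Content of a record.** Section 9.2 names the items to document: "Information relating to the AE such as onset and cessation date, intensity, seriousness, relationship to study drug, and outcome". Section 15.1 says of intensity: "The maximum intensity encountered during the evaluation period should be checked". Section 9.3 has the eCRF updated as new information arrives.
- **Causality.** Section 15.1 gives alternative items under the not-related category, any one of which is enough. One is: "An event that precedes the first administration of study drug".
- **Worsening.** Section 9.1.1: "AEs may also include worsening of an existing symptom or condition".

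SAP 1.1 records that the study was terminated with 3 subjects randomized in the first cohort, and that only listings will be produced.

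**The concern.** A treatment-emergent definition normally has two limbs: onset after treatment starts, and worsening after treatment starts of something already present. SAP 11 has only a timing limb. In ventilated infants born before 27 weeks an event could well be open at the time of dosing, and an acute effect of the infusion could then appear as deterioration of that event. Protocol 6.1 itself describes the reasons for stopping an infusion largely as acute worsening or acute change.

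Two of the primary endpoints in SAP 2.2.1 concern treatment-emergent events and treatment-related events. With no summaries planned, the per-event flag is the only output that represents the first of these, and the causality entry is the only output that represents the second. If a post-dose deterioration is folded into a record with a pre-dose onset, the flag can be wrong and the causality entry can be pulled the same way.

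**Working it through.** The documents give no figure to reproduce and no formula applies. The check follows one hypothetical event through the rules. Suppose hypotension of Grade 1 begins 20 hours before dosing and reaches Grade 3 two hours after it.

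**Step 1: is it on record before dosing?** Yes. Collection starts at consent (3.3.2.4), and screening can precede Baseline by up to 48 hours (7.1).

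**Step 2: how is the deterioration recorded?** The protocol allows two routes and does not choose between them.

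- *Route A, one record updated.* Sections 9.2, 9.3 and 15.1 together fit this route: one onset date, one intensity, the maximum entered, the eCRF updated. The record shows a pre-dose onset and Grade 3. Nothing among the named fields shows that the rise to Grade 3 followed the infusion.
- *Route B, a second record.* Section 9.1.1 permits worsening to be an event in its own right. The second record has a post-dose onset and Grade 3.

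**Step 3: what flag does SAP 11 give?** The sentence speaks of assessments that occur. It does not say onset, and it does not address an event that spans the infusion.

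| Recording | Occurrence read as onset | Occurrence read as present at any time on or after the infusion |
|---|---|---|
| Route A | Not treatment-emergent | Treatment-emergent, but so is every event still open at dosing, worsened or not |
| Route B, second record | Treatment-emergent | Treatment-emergent |

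The post-dose deterioration is missed in one of the four cells: a single record with the onset reading. In the other Route A cell the flag errs in the opposite direction for events that did not worsen.

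**Step 4: what happens to causality?** On Route A the record meets the not-related item about preceding the first administration. The same event can also fit items under the possible category in 15.1, such as timing relative to study drug or an unexpected degree of severity. The categories overlap, and 15.1 leaves the estimate to the Investigator. On Route B the item about preceding administration does not apply to the second record.

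**Step 5: do other passages force Route B?** Not in general. The examples and exclusions in 9.1.1 are tied to the start of the study, not to dosing, and its wording is permissive. The instruction in 15.1 to report a clinically significant change from Baseline covers diagnostic and laboratory tests. Section 3.3.2.2 requires treatment-emergent findings to be recorded as events, but it sits under physical examination and chest x-ray. Section 6.3 requires a dose-limiting toxicity to be entered as an event, but only after it has been judged one.

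**Step 6: what reaches the reader?** All adverse events are listed whatever their flag (SAP 11.2). Infusion start and stop times are listed (SAP 11.1), and vital signs are listed with date and time (SAP 11.5). On Day 1 vital signs are taken before, midway through and just after dosing, then at least hourly for 4 hours (Protocol 3.3.2.3). In the example, blood pressure at about two hours would be visible there even if the flag were wrong.

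**The case against.** The strongest case on the other side is that nothing here is automatic and little depends on it. Section 9.1.1 allows worsening to be recorded separately. SAP 11 does not equate occurrence with onset. Section 9.2 introduces its fields as examples, and the eCRF is not among the documents, so a field for the date of a grade change cannot be ruled out. The SAP covers 3 infants with listings only, and a reader can check each infant against timed vital signs, laboratory values and respiratory support. All of this stands. It limits the point to a possible misflag, but it does not supply the missing rule.

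A reader might infer more than the documents support in four ways:

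- *That 15.1 makes such an event not related.* It does not. The event meets one item in that category and can also meet items under possible, and the Investigator decides.
- *That the dose-limiting toxicity definition loses these events.* Only the first of the three listed criteria in Protocol 6.3 is framed as a treatment-emergent event. The liver and respiratory criteria are not, and the respiratory one names worsening. The SAP sentence sets an indicator in a listing and is not stated to govern those decisions.
- *That the error always favours the drug.* Under single-record handling with the onset reading it can only omit. Under the other reading it over-flags. The same rule applies to placebo.
- *That an incidence is shifted by some number of percentage points.* No incidence is computed under this SAP. Neither document says how often an event is open at dosing or worsens afterwards.

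**Conclusion.** The point holds as a gap in a definition. SAP 11 does not say how to flag an adverse event that spans the infusion, and no passage requires a new record when an open event worsens after dosing. Kept as one record, with occurrence read as onset, the event is flagged not treatment-emergent and meets one not-related item, and the named fields hide the timing of the higher grade.

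The size is small: the indicator, and possibly the causality entry, for any such event among 3 randomized infants. Every event stays in the listing. The gap is still worth closing, because the flag is the only output for one of the primary endpoints and the correction is cheap.

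The conclusion assumes that the eCRF has no field dating a change of grade, and that at least one site could record deterioration as an update. The documents neither confirm nor exclude either. They also do not say whether any of the 3 infants had an event open at dosing.

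**What to change.** Replace the sentence in SAP 11, as it applies to adverse events, with: *An AE is treatment-emergent if its onset is on or after the start of infusion, or if it was present before infusion and increased in intensity on or after it.*

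Before database lock, check every adverse event with pre-dose onset against source for the 3 randomized infants and set the flag accordingly. SAP 5 places unblinding after lock, so the check can be done blinded if lock has not yet happened.

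If enrolment were ever resumed, Protocol 9.2 and 15.1 should also require a new record, with date and grade, when an open event worsens after dosing. The not-related item about preceding the first administration should then be limited to events that did not worsen after dosing. In the terminated study these protocol edits would achieve little.

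The cost is one sentence and a review of a handful of records at most. The downside is that some natural progression of disease will be flagged treatment-emergent, under the same rule in both arms.
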